4.3.2 Data collection with intervention recipients and intervention	
non-recipients	76

	4.3.3 Data collection with the delivery partner (HUL)	81
	4.3.4 Data collection with the reward partners	82
	4.3.5 Data collection with City of Wolverhampton Council	84
	4.3.6 Data collection - timelines	85
	4.3.7 Risks	86
	4.4 Qualitative Data Analysis	88
6.	Limitations and generalisability	89
7.	Appendices	90
	Appendix A - Alternatives to Intake24	90
	Appendix B - Additional information on power calculations	91
	Appendix C - Recommended dietary intake according to the Recommended	ł
	dietary intake according to the Government Dietary Recommendations	94
	Appendix D - Possible additional analysis subject to contractual agreement	94

Executive Summary

Promoting healthy eating and more physical activity in England can help to improve population health. To promote these health behaviours the Department for Health and Social Care (DHSC) commissioned HeadUp Labs (HUL) to develop and implement an app-based financial incentive scheme to provide rewards to people contingent on performing behaviours related to healthy diets and physical activity. The Behavioural Insights Team (BIT) will design and conduct an independent mixed-methods evaluation of the financial incentive scheme including an impact, and an implementation and process evaluation. This document summarises BIT's plans for the impact evaluation.

This document includes more detail than what would normally be covered in an academic protocol for an impact evaluation, as it also captures considerations around the implementation, mitigation strategies, or the rationale for specific design choices.

Summary of the impact evaluation

To test the effectiveness of the financial incentives, BIT will run a randomised controlled trial (RCT). The main research question this study aims at answering is **whether the incentive scheme improves physical activity (PA) and diet healthfulness.** This will be a clustered randomised trial, in which randomisation happens at the household level.

Participants will be adults, recruited from the community in Wolverhampton. All participants will receive access to the HeadUp app and a wearable tracker if they do not already own one. Participants will complete a baseline period during which they will familiarise themselves with the app and wearable and provide baseline data, after which they will be randomised to one of four conditions:

- A. Control group: Access to the HeadUp app and the wearable tracker
- **B.** Intervention groups: On top of the HeadUp app and the wearable tracker participants will receive a financial incentive intervention for the entire duration of the trial with:
 - **B.1** low value incentives, i.e. low £ per point ratio
 - $\circ~$ **B.2** medium value incentives, i.e. medium £ per point ratio
 - **B.3** high value incentives, i.e. high £ per point ratio

A detailed description of the intervention and baselining logic is provided separately by HUL.

The primary outcomes consist of **2 physical activity outcomes** and **4 dietary outcomes**. The primary physical activity outcomes will be (i) moderate and vigorous physical activity (MVPA) in minutes per day and (ii) daily steps measured objectively through a wearable device. The primary dietary outcomes will be daily intake of (i) fruit and vegetables (g/day), (ii) fibre (g/day), (iii) saturated fat (% of food energy intake) and (iv) free sugars (% of food energy intake) measured through 24 hour dietary recalls. Secondary outcomes will be (i) daily energy expenditure as measured by the wearable, (ii) daily energy intake as measured by 24 hour dietary recalls (Intake24 surveys), (iii) a healthy eating score based on consumption of key food groups, macro- and micronutrients, and (iv) self-reported weight.

Exploratory outcomes will include (i) motivation to change PA and dietary intake as well as (ii) potential unintended health consequences (i.e. mental health and sleep duration). The motivational and mental health outcomes will be measured by in-app mini-surveys, whereas sleep duration will be measured by the wearable.

All primary and secondary outcome data will be collected at the baseline (i.e. pre-randomisation), at one month, three months, and at five months after the randomisation. The exploratory outcomes will be collected at the baseline and at five months after the randomisation.

The pre-planned primary analysis will compare the 2 physical activity outcomes and 4 dietary outcomes at five months post-randomisation between the control group and the three pooled financial incentives groups (i.e. being offered any level of financial incentive).

The pre-planned secondary analyses (see Table 11 for details) will focus on investigating (i) energy intake, weight, energy expenditure and a healthy eating score; ; (ii) shorter-term impact of the intervention (i.e. the impact at one month and three months after randomisation) on the primary outcomes; (iii) the impact of the intervention intensity (i.e. low, medium, high incentive level) on primary outcomes five months after randomisation.

The pre-planned exploratory analysis will investigate (i) the intervention impact on the primary outcomes at five months for various subgroups of interest (i.e. deprivation, sex, age, ethnicity, baseline PA level, and baseline dietary intake¹, see Table 12 for details), (ii) the intervention impact on participants' motivation to increase PA and improve dietary intake at five months (subject to contractual agreements, see **Section 2.3.3.1** for details), and (iii) whether the interventions had any unintended health consequences on sleep quality and mental well-being at five months.

Outcomes will be presented as the absolute difference between the control and intervention group.

Summary of the implementation and process evaluation

A mixed method implementation and process evaluation (IPE) will be conducted alongside the impact evaluation. Whilst the impact evaluation will test the effectiveness of the financial incentive scheme, the IPE will aim to identify why and how the intervention achieves - or fails to achieve - the expected outcomes in relation to the Theory of Change (ToC). The IPE will also explore potential desirable and undesirable unintended consequences. The IPE will focus particularly on

¹ Subgroup analysis of baseline PA level and baseline dietary intake are subject to contractual agreement.

understanding issues pertaining to (i) reach of the intervention, (ii) engagement with the intervention, (iii) mechanisms of action, (iv) and implementation and feasibility.

The methods used for the IPE will be (i) rooted in the details of the Theory of Change and the user journey, (ii) mindful of the needs of the research participants, especially those from more deprived communities, and (iii) form part of an integrated plan with the impact evaluation, so that the analysis from the IPE can help to explain any significant or null effects observed. Based on these three principles, the mixed-methods IPE will triangulate findings from qualitative interviews and focus groups and quantitative analyses of in-app data. Comparing and contrasting between these multiple sources of data will allow us to (i) gain insights across a large number of individuals whilst also (2) developing an in-depth understanding of individual experiences.

1. Introduction

Behavioural risk factors represent the largest opportunity to reduce health burdens across the population, making up more than 50% of the preventable Disability Adjusted Life Years (DALYs) as estimated by the Global Burden of Disease study.² Furthermore, behavioural risk factors have a steep social gradient, and are therefore a key contributor to health inequities.

Unhealthy diets and low levels of physical activity are associated with a wide range of chronic conditions, including excess weight, cardiovascular disease, type 2 diabetes, and some forms of cancer.^{3 4} Despite the importance of eating healthily and being physically active, it is estimated that nearly 40% of adults do not reach the recommended 150 minutes of physical activity per week⁵, 72% of adults consume less than five portions of fruit and vegetables per day⁶, and on average adults consume more energy, saturated fat, and sugar than recommended⁷.

In the UK, the Eatwell guide and the Chief Medical Officers (CMO) guidelines for physical activity provide recommendations for how adults can achieve a healthy diet and healthy physical activity levels. To support adults in England to translate these recommendations into practice, the DHSC has decided to pilot an app-based financial incentive scheme to incentivise adults to eat healthier diets and be more physically active. The financial incentive scheme will be piloted in Wolverhampton and its potential effectiveness will be evaluated to inform decisions about whether and how to further scale the intervention.

² Global Burden of Disease Data (link)

³ ibid.

⁴ Scarborough P, Bhatnagar P, Wickramasinghe KK, Allender S, Foster C, Rayner M. The economic burden of ill health due to diet, physical inactivity, smoking, alcohol and obesity in the UK: an update to 2006–07 NHS costs. Journal of public health. 2011 Dec 1;33(4):527-35.

⁵ Sport England Active Lives Adult Survey November 2019/20 Report (link)

⁶ Health Survey for England 2018 (link)

⁷ National Diet and Nutrition Survey 2014/15 to 2015/16 (link)

DHSC commissioned HeadUp Labs (HUL) to develop the financial incentive scheme and deliver it through their digital healthy-lifestyle app. The Behavioural Insights Team (BIT) will act as an independent evaluator of the financial incentive scheme to understand whether, and to what extent, financial incentives can motivate behaviour change.

BIT will also conduct an implementation and process evaluation of the scheme to gain an in-depth qualitative understanding of how users viewed and interacted with the intervention, the mechanisms through which the intervention worked (or the barriers for why it did not), and to identify opportunities to further improve the intervention. This will be done using both qualitative (interviews and focus groups) and quantitative methods (analysis of app-based metrics).

This document sets out the methodology for how BIT intends to evaluate the financial incentive scheme. This document should be read in conjunction with the *Intervention design plan by HUL.*

2. Impact Evaluation

2.1 Objectives and hypotheses

The primary objective of the impact evaluation study is to assess the effectiveness of the financial incentive scheme at

• increasing moderate-vigorous physical activity (MVPA minutes/day and steps/day) among adults recruited from the general public in Wolverhampton.

and

 improving the healthfulness of the diet (fruit and vegetables in g/d, fibre in g/d, free sugars in % of food energy/day, and saturated fat in % of food energy/day) among adults recruited from the general public in Wolverhampton.

BIT's impact evaluation will be designed to test the hypothesis that financial incentive schemes significantly increase physical activity (PA) levels (throughout, this is defined through our two primary outcomes for physical activity) and improve the healthfulness of recipients' dietary intake (throughout, this is defined through our four primary outcomes for diet), by comparing the behaviour of users allocated to a control group (no financial incentives offered) to the behaviour of users allocated to the pooled treatment groups (low, medium or high level of financial incentive offered).

The secondary research questions include:

- **Broader effects on PA and diet:** Does offering financial incentives significantly affect participants' energy expenditure, energy intake, their score on a healthy eating score based on consumption of key food groups, macro-and micronutrients, and weight) five months after randomisation?
- **Shorter-term effects:** Does offering financial incentives effectively improve participants' dietary intake and PA in the shorter term (one and three months after randomisation), comparing the behaviour of users allocated to a control group (no financial incentives offered) to the behaviour of users allocated to the pooled treatment groups (low, medium or high level of incentive offered)?
- **Optimal incentive value:** Do different levels of financial incentives achieve different effect sizes on participants' dietary intake and PA level five months after randomisation, comparing the behaviour of users allocated to a control group (no financial incentives offered) to the behaviour of users allocated to

each treatment group (low, medium and high level of incentive offered)?

The exploratory research questions include:

- **Subgroup analyses:** Does the incentive scheme also work among specific population subgroups five months after randomisation in terms of improving dietary intake and PA (focusing on primary outcomes), comparing the behaviour of users allocated to a control group (no financial incentives offered) to the behaviour of users allocated to the pooled treatment groups (low, medium or high level of incentive offered)?
- Longer-term effects on motivation to change: Does offering financial incentives effectively increase participants' motivation to improve dietary intake and to increase PA level five months after randomisation, comparing the motivation level of users allocated to a control group (no financial incentives offered) to that of users allocated to the pooled treatment groups (low, medium or high level of incentive offered)?
- Unintended consequences: Does the incentive scheme have any significant impact on participants' sleep or mental health five months after randomisation, comparing the behaviour of users allocated to a control group (no financial incentives offered) to the behaviour of users allocated to the pooled treatment groups (low, medium or high level of incentive offered)?

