2.3.2.3 Secondary outcome - weight

Although the financial incentive scheme is not a weight loss app, measuring weight is important to help assess whether this healthy eating and physical activity intervention could also help to reduce the prevalence of obesity or indeed to rule out potential unintended consequences on weight.

³⁴ Scheelbeek P, Green R, Papier K, Knuppel A, Alae-Carew C, Balkwill A, Key TJ, Beral V, Dangour AD. Health impacts and environmental footprints of diets that meet the Eatwell Guide recommendations: analyses of multiple UK studies. BMJ open. 2020 Aug 1;10(8):e037554.

³⁵ Scheelbeek P, Green R, Papier K, Knuppel A, Alae-Carew C, Balkwill A, Key TJ, Beral V, Dangour AD. Health impacts and environmental footprints of diets that meet the Eatwell Guide recommendations: analyses of multiple UK studies. BMJ open. 2020 Aug 1;10(8):e037554.

Participants will be asked to self-report their current weight at the baseline and each measurement timepoint. The app will encourage participants to weigh themselves when entering weight data.

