Standard deviation data source	n = 19,898 UK users, whose demographic and obesity profiles are most similar to the target population of this trial ⁴² (HeadUp Labs, 2019)		n = 475 UK adults (19-64 years old) ⁴³ (National Diet and Nutrition Survey 2020)			
Standard deviation estimate	26 min/day	4,096/day	190 g/day	7.5 g/day	6.3 %	3.2 %
Effect size range from prior literature	0.02 to 0.4 SD units ⁴⁴		0.04 to 0.58 SD units ⁴⁵			
Target minimum detectable effect size in SD (MDES)	0.2 SD units		0.11 SD unit			
Target MDES in absolute terms (note: these are all larger than the effect size we estimate to be powered for)	5.2 MVPA min/day	819 steps/day	21 g/day	0.83 g/day	0.69 %	0.35 %
Assumed attrition rate	See Table 7 (Section 2.4.2.3)					

⁴² We only included user whose age profile matches that of the target population, i.e. 18-65 years old, and 69% of the included users were overweight or obese, highly comparable to the proportion in Wolverhampton, which is 70% according to the UK's latest obesity statistics report.

⁴³ Public Health England. (2021). National Diet and Nutrition Survey: Diet, nutrition and physical activity in 2020 - a follow-up study during COVID-19. Retrieved from https://www.gov.uk/government/statistics/ndns-diet-and-physical-activity-a-follow-up-study-during-covid-19

⁴⁴ Mitchell et al. (2020). Financial incentives for physical activity in adults: systematic review and meta-analysis. *British Journal of Sports Medicine*, 54(21), 1259-1268.

⁴⁵ Pomerleau, J., Lock, K., Knai, C., & McKee, M. (2005). Interventions Designed to Increase Adult Fruit and Vegetable Intake Can Be Effective: A Systematic Review of the Literature. *The Journal of Nutrition*, *135*(10), 2486–2495. doi: 10.1093/jn/135.10.2486

Adjustment for baseline covariates	Corr. coef = 0.25-0.75 (0.5 as most realistic)			
Target power	80%			
Adjusting for multiple comparisons	Bonferroni adjustment ⁴⁶ for primary outcomes by category (one comparison each of all incentive arms [pooled] vs. control; the number of adjustments is 2 for PA activities and 4 for dietary outcomes)			
Allocation ratio across arms post-attrition	3 participants in the control arm for every 1 participant in each intervention arm			
Cluster size assumptions for household-level randomisation	Sample will comprise: 39% 1-adult HHs, 41% 2-adult HHs, and 20% 3-adult HHs, with all adults in a HH signing up			
Assumed ICC (more details in Appendix B)	0.2-0.5 (0.2-0.4 as more realistic)			

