Number of overall users required for smaller dietary outcome target MDES at the 5m mark analysis stage	4,200 (2,100 in control; 700 per intervention arm)			

⁴⁶ The Benjamini-Hochberg false discovery adjustment will be applied during analysis of primary outcomes, but as it is not possible to apply this before having the data, the more conservative Bonferroni adjustment provides an upper bound on power here.

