2.6.3.8 Analytical strategy for the secondary analysis: Impact of different incentive levels

The impact of each incentive level on the primary outcomes will be assessed using the same approach as the one for the primary analysis but we will categorise the treatment indicator differently. In these regressions, *Treatment*, will be a series of

three dummy variables, each of them taking value 0 for households (or users for the individual level randomisation) allocated to the control group, and 1 for households (users) allocated to the specific treatment group for low, medium or high levels of incentives.

This approach will allow us to statistically compare the effect of each incentive with the control group.

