The impact of offering incentives (compared to not offering any incentives) on exploratory outcomes at the 5 months mark will be assessed using similar methods as the ones for the primary analysis. We will not impute values at baseline or at 5 months. If there are missing values for an exploratory outcome at baseline, we will add an indicator variable for missingness to the set of covariates so that all individuals with non-missing values for the outcome at 5 months can be included.

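### WHO-5, sleep duration and weight are compared with control only with the three incentive levels pooled, although the trial asks which incentive value works best

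*Protocol*

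**What the plan says.** Section 2.1 sets the unintended-consequences question as the impact on "sleep or mental health five months after randomisation, comparing the behaviour of users allocated to a control group (no financial incentives offered") with that of "users allocated to the pooled treatment groups (low, medium or high level of incentive offered"). Section 2.6.3.10 repeats the contrast for the analysis: "The impact of offering incentives (compared to not offering any incentives) on exploratory outcomes at the 5 months mark". Section 2.6.3.6 does the same for the secondary outcomes, which include weight. Section 2.3.2.3 says that weight is measured partly "to rule out potential unintended consequences on weight".

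Section 2.1 also asks, under optimal incentive value, "Do different levels of financial incentives achieve different effect sizes" on diet and physical activity. Section 2.6.3.8 answers with three treatment dummies, one per level: "The impact of each incentive level on the primary outcomes will be assessed using the same approach as the one for the primary analysis". Table 11 lists the six primary outcomes for that analysis and no others.

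The planned numbers at five months are "4,200 (2,100 in control; 700 per intervention arm"), that is, "3 participants in the control arm for every 1 participant in each intervention arm".

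**The concern.** By section 2.2.1 the three incentive arms differ only in the size of the rewards, and the Introduction says the pilot is to inform whether and how the scheme is scaled. Reward size is therefore the feature on which a later decision would turn. An unintended effect may well depend on it. The protocol's own example in 4.1.2, more spending on unhealthy food because people have more money, is a mechanism that could grow with the value paid.

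As planned, the report would give the six primary outcomes at each level, but for well-being, sleep and weight a single figure averaged over low, medium and high. If the high value looked best on the primary outcomes, no planned estimate would show what happened to these three outcomes at that value.

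**Working it through.** **Inputs.** From 2.4.2.1 (Table 5) and 2.4.2.2: 2,100 control and 700 per incentive arm; household ICC 0.3; baseline correlation 0.5; households of 1, 2 and 3 adults in shares 39/41/20%. Mean household size is 0.39 + 0.82 + 0.60 = 1.81, so the design effect is 1 + 0.81 × 0.3 = 1.243. The protocol prints no alpha; I assume two-sided 5%. It gives no SD for WHO-5, sleep or weight, so effects are in SD units and the ICC and correlation are borrowed from the primary-outcome calculation.

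**Standard errors (SD units).** SE = sqrt((1 − 0.5²) × 1.243 × (1/n1 + 1/n2)).
- Pooled v control (2,100 v 2,100): 0.0298
- One level v control (700 v 2,100): 0.0421, or 1.41 times the pooled SE
- High v low (700 v 700): 0.0516, or 1.73 times the pooled SE

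**Check against the plan's own figures.** Detectable effect at 80% power = (z + 0.842) × 0.0298 × SD, with alpha 0.05/4 for diet (z = 2.498) and 0.05/2 for physical activity (z = 2.241). Fruit and vegetables: 3.339 × 0.0298 × 190 = 18.9 g/day (stated 18.7). MVPA: 3.083 × 0.0298 × 26 = 2.39 min/day (stated 2.4). All six stated values are reproduced within 3%.

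**Effect d in the high arm only.** The pooled difference is d × 700/2,100 = d/3. Power = Φ(difference/SE − 1.96), plus a negligible opposite tail.

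| d (SD) | Pooled difference | Power, pooled | Power, high v control |
|---|---|---|---|
| 0.10 | 0.033 | 20% | 66% |
| 0.15 | 0.050 | 39% | 94.5% |
| 0.20 | 0.067 | 61% | 99.7% |
| 0.25 | 0.083 | 80% | >99.9% |

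The pooled test reaches 50% power at d = 3 × 1.96 × 0.0298 = 0.175 SD and 80% at 3 × 2.80 × 0.0298 = 0.25 SD. High v control reaches 80% at 2.80 × 0.0421 = 0.118 SD.

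The ratio of the two test statistics is (d/3)/0.0298 divided by d/0.0421, which is sqrt(2)/3 = 0.47. It does not depend on the SD, ICC, baseline correlation or total N while the 3:1:1:1 allocation holds. An effect with 80% power in the direct contrast thus has 26% in the pooled one.

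**Graded effect (d/3, 2d/3, d for low, medium, high).** The pooled difference is 2d/3. At d = 0.10 SD, power is 61% pooled and 66% for high v control, so little is lost. The pooled estimate is still a third below the high-arm effect.

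**Uniform effect d at all levels.** At d = 0.10 SD, power is 92% pooled and 66% for high v control, so pooling is better.

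**Sensitivity.** With a size-weighted design effect of 1.335, the d = 0.15 high-arm-only case gives 37% v 93%. With alpha 0.025 (two outcomes within the research question, as Appendix B would adjust), it gives 29% v 91%, and the 50% point for the pooled test moves to about 0.20 SD.

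**The case against.** A reader might infer that harm at the high level would mostly be missed. The documents do not support that in general. It needs an effect confined to the high arm and smaller than about 0.175 SD; at 0.20 SD the pooled test has 61% power and at 0.25 SD 80%. Arms that differ only in reward size suggest a graded effect at least as naturally, and there pooling costs little. With a Bonferroni correction over three levels, high v control at d = 0.10 SD drops to 49%, below the 61% of the pooled test.

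A reader might also infer that the plan treats harm less carefully than benefit. The line it draws is between primary and non-primary outcomes: energy expenditure, energy intake, the healthy eating score and motivation are pooled too. Nor are these three pure harm outcomes. Section 2.3.3.2 allows for well-being effects in either direction and for better as well as worse sleep, and 2.3.2.3 names a possible reduction in obesity first.

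There is other oversight: a clinical safety group and safety officer, an ad hoc data monitoring committee, dashboards split by arm that include BMI and sleep, and interviews sampled by arm. Harm by arm is therefore not invisible. The sections also agree with each other, and extra contrasts for non-primary outcomes are often left to a SAP.

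All of this limits the size of the point. It does not remove it. None of those safeguards is a planned estimate by level against control with a confidence interval. On the contrast itself the protocol is not silent: it states the pooled one in 2.1, 2.6.3.6 and 2.6.3.10.

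**Conclusion.** The point stands as a worthwhile, inexpensive improvement. The plan would report the six primary outcomes by incentive level, but only a level-averaged effect for the three outcomes that serve, at least in part, as checks for unintended consequences. The pooled estimate shows one third of an effect confined to the high arm and two thirds of the high-arm effect if the effect is evenly graded. It represents the high level correctly only if the effect is the same at all levels.

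The loss of power is large only in the first case (20% v 66% at 0.10 SD, 39% v 94.5% at 0.15 SD). In the second the problem is the estimate, not the power.

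These figures assume the planned 2,100 and 3 × 700 with data on these outcomes. Actual numbers may differ, since WHO-5 and sleep data are not required for randomisation. By the randomised numbers in Table 6 the high arm is 1,900/6,100 = 0.31 of the pooled group, so the dilution is much the same. Which pattern holds is not known, and the documents do not say that the level would be chosen on the 2.6.3.8 results alone.

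**What to change.** In 2.1, 2.6.3.6 (for weight), 2.6.3.10 and Table 11, keep the pooled comparison and add the three-dummy model of 2.6.3.8 for WHO-5, sleep duration and weight at five months. Report low, medium and high v control, each with a 95% CI, labelled exploratory, beside the by-level results for the primary outcomes. State how these estimates relate to the multiplicity rule in Appendix B.

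The cost is one re-coded treatment term in models already planned, with no new data. It adds nine exploratory estimates (three levels × three outcomes), each with an SE about 1.4 times the pooled one, and so some added chance of a false signal. A high v low contrast is optional; it goes beyond 2.6.3.8 and its SE would be about 1.7 times the pooled one.
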